4.9 Annual Years 2-5 Post-Procedure Follow-up Assessment

Subjects will be seen in the office at 2, 3, 4 and 5 years (\pm 60 days) post-procedure. The following evaluations will be completed and data collected on the Follow-up eCRF:

1. NYHA classification
2. 12 lead ECG
3. Hematology/chemistry data
4. Echocardiography examination (TTE)
5. Relevant medications
6. Adverse events/device deficiency

Medtronic Controlled Information

5 Subject Accountability

5.1 Missed Follow-up Visits

Every effort should be made to ensure subjects return to the clinic for all protocol required follow-up visits (excluding 18 and 30 month phone visits). If the subject is unable to return for an in-person clinic visit, the Investigator (or designee) must document the reason the subject was unable to complete the visit and, if applicable, follow the requirements for deviation reporting as outlined in Section 6.9. The Investigator should also make every effort to contact the subject within the visit window, to collect the subject's vital status (recorded on the Follow-up eCRF) as well as information related to potential adverse events (recorded on the AE eCRF).

5.2 Unscheduled Follow-up Visits

If a subject returns to the institution between the protocol-required follow-up visits, the visit will be treated as an unscheduled visit and the assessments completed at this visit will be done at the discretion of the investigator. The reason for the unscheduled visit, as well as any assessment data will be recorded on the Follow-up eCRF and AE data on the AE eCRF.

5.3 Subject Withdrawal or Discontinuation

It is the subject's right to withdraw at any time from the trial and for any reason without sanction, penalty or loss of benefits to which the subject is otherwise entitled, and without jeopardizing their future medical care. The investigator may withdraw the subject at any time to protect the health, safety or welfare of the subject. At the last point of contact (if outside a trial-required visit), the subject's vital status should be recorded on a Trial Exit eCRF, and every effort should be made to collect the status of any ongoing adverse events. Sites shall request permission from the subject to follow-up outside of the trial, if issues arise with the investigational device safety or performance.

The subject may only be considered lost to follow-up after all efforts to obtain compliance are exhausted. At a minimum, four attempts must be made to contact the subject and documented in the subject's trial records:

- 3 telephone attempts to the subject's last known phone number, and if unsuccessful,
- 1 certified letter from the PI to the subject's last known address

If the site is unable to reach the subject after the documented attempts, the site should make every attempt to verify the subject's vital status (alive or deceased).

All subjects will be encouraged to remain in the trial through the last follow-up visit. Subjects who discontinue participation prematurely will be included in the analysis of results, but will not be replaced in the enrollment of total trial subjects. If the subject discontinues participating in the trial prior to

Medtronic Controlled Information

completing the trial requirements, the reason for withdrawal will be recorded in the subject’s trial records and on the Trial Exit eCRF.

There are many scenarios in which a subject may exit the trial. Table 2 below details how the data will be handled for each scenario.

Table 2: Trial exit scenarios

Scenario	Follow-up Required	CRFs Required
Subject enrolled (informed consent signed), but the study device(s) (sizer, handle, valve) never contacts subject, and no Model 400 valve is implanted	None	-Inclusion/Exclusion eCRF -Baseline eCRF (as applicable) -AE eCRF (as applicable) -Unscheduled eCRF (as applicable) -Trial Exit eCRF
Subject enrolled, the study devices(s) (sizer, handle, valve) comes into contact with the subject (i.e., passes the body plane) but no Model 400 valve is implanted	30 days post-attempted implant for safety only	-Inclusion/Exclusion eCRF -Baseline eCRF (including labs/echo) -Implant eCRF -Discharge or 30 Day eCRF (including labs/echo) -AE eCRF (as applicable) -Other unscheduled eCRFs (as applicable) -Trial Exit eCRF
Subject enrolled, implanted with Model 400 valve, and exits the trial early due to explant	30 days post-explant for safety only	-All required/ unscheduled eCRFs through last visit completed -Valve Reintervention eCRF -AE eCRF (as applicable) -Trial Exit eCRF
Subject enrolled, implanted with Model 400 valve, and exits the trial early due to any of the following: 
 - Lost to Follow-up - Death - Withdrawal 	Through point of death, withdrawal, or last visit completed	-All required/ unscheduled eCRFs through last visit completed -AE eCRF (as applicable) -Trial Exit eCRF
Subject enrolled, implanted and completes the trial requirements	Through 5 year follow-up	-All required/ unscheduled eCRFs -AE eCRF (as appropriate) -Trial Exit eCRF

6 Trial Assessments

6.1 Baseline

A careful medical history and physical examination should be taken prior to the implant procedure. Attention should be taken to document any chronic illnesses and pre-existing cardiac arrhythmias.

For any cardiac interventions, the date of the most recent intervention should be captured.

Use of the following medications will be collected at baseline; see Section 6.6 for additional information about specific data collection for medications:

- Anticoagulants
- Antiplatelets
- Aspirin (including Carbasalate Calcium)

Data to be collected at baseline:

- Gender
- Age at time of enrollment (in years and months)
- Race/Ethnicity- to be collected per the FDA Guidance for Collection of Race and Ethnicity Data in Clinical Trials (2005), in support of regulatory submissions in the United States (FDA) and Japan (PMDA). This requirement will be waived for subjects participating in countries where it is unlawful to collect race and ethnicity data.
- Co-existing cardiovascular conditions (including, but not limited to congestive heart failure, cardiomyopathy, peripheral vascular disease, coronary artery disease, previous myocardial infarction (MI), atrial enlargement, cardiac arrhythmias)
- Previous cardiovascular operations (including, but not limited to implanted cardiac device (pacemaker, defibrillator, CRT device), coronary artery bypass, coronary artery angioplasty, percutaneous valvuloplasty, operative valvuloplasty, previous aortic heart valve replacement, annuloplasty)
- Co-existing chronic and transient medical conditions (including, but not limited to liver, kidney, lung disease, substance abuse (alcohol/drug), diabetes (Type I or Type II), hypertension, endocarditis)
- 12-Lead ECG to collect cardiac rhythm (sinus rhythm, atrial fibrillation, atrial flutter, heart block, etc.)
- NYHA Classification
- STS risk score
- Hematology/chemistry, including serum creatinine to allow for the calculation of a EuroSCORE.

Medtronic Controlled Information

For female subjects of child-bearing potential, a pregnancy test will be done at baseline to confirm that the subject is not pregnant. Subjects exempt from this requirement are those who have been surgically sterilized, who are infertile, or who have been post-menopausal for at least 12 months (no menses).

6.1.1 STS Risk Scores

The Society of Thoracic Surgeons’ risk models predict the risk of operative mortality and morbidity after adult cardiac surgery on the basis of patient demographic and clinical variables.

<http://riskcalc.sts.org/stswebriskcalc/#/>

The online calculator provides additional guidance for each of the parameters used to calculate the scores. Risk of Mortality and Risk of Morbidity or Mortality scores should be recorded on the Baseline eCRF. The STS Risk Scores should be printed from the online calculator and filed as source documentation for trial subjects.

6.2 NYHA Functional Classification

The New York Heart Association (NYHA) Functional Classification is a system for defining cardiac disease and related functional limitations into four broad categorizations as defined in Table 3.

Table 3: New York Heart Association (NYHA) Classification

Class I	Subject with cardiac disease but without resulting limitations of physical activity. Ordinary physical activity does not cause undue fatigue, palpitation, dyspnea, or anginal pain.
Class II	Subjects with cardiac disease resulting in slight limitation of physical activity. They are comfortable at rest. Ordinary physical activity results in fatigue, palpitation, dyspnea, or anginal pain.
Class III	Subjects with cardiac disease resulting in marked limitation of physical activity. They are comfortable at rest. Less than ordinary physical activity causes fatigue, palpitation, dyspnea, or anginal pain.
Class IV	Subjects with cardiac disease resulting in inability to carry on any physical activity without discomfort. Symptoms of cardiac insufficiency or of the anginal syndrome may be present even at rest. If any physical activity is undertaken, discomfort is increased.

NYHA classification will be assessed at baseline, discharge (up to 30 days), and all in-office follow-up visits, and the results recorded on the appropriate eCRF. The NYHA classification should be assessed by a medical doctor, physician assistant or nurse practitioner.

6.3 12-Lead ECG

A standard 12-Lead ECG should be taken at baseline, discharge (up to 30 days), and all in-office follow-up visits to assess cardiac rhythm, noting any cardiac arrhythmias and indications for pacing. The site will record ECG data on the appropriate eCRF.

The Investigator or Sub-Investigator should review and sign/date each 12-lead ECG recording conducted as part of the trial requirements, verify or correct any automated diagnosis generated by the ECG machine, and note the clinical significance of any diagnosis/finding of the ECG. Any new abnormalities should be recorded on an Adverse Event eCRF.

6.4 Echocardiography

Transthoracic echocardiography (TTE) is required at baseline, discharge (up to 30 days), and all in-office scheduled follow up visits. The site will record echocardiography data on the Site Echo eCRF.

A peri-procedural Transesophageal Echocardiogram (TEE) is required before the subject leaves the operating room/theater to assess the valve implant and evaluate/characterize any paravalvular leak and peak /mean gradient. The site will record the TEE data on the Implant eCRF.

All TTE exams will be sent to the Echo Core Lab for central assessment; the Echo Core Lab will record the central assessment on the Echo Core Lab Assessment eCRF.

Details of the Echocardiography methods are provided in Appendix G: Echocardiographic Procedures. Additional information regarding the Echo Core Lab can be found in Section 16.1.

6.5 Hematology/Chemistry

This section describes the laboratory parameters required at baseline and at each postoperative in-office interval.

6.5.1 Hematology/Clinical Chemistry

- Complete Blood Count:
 - White Blood Cell (WBC) Count
 - Red Blood Cell (RBC) Count
 - Hemoglobin
 - Hematocrit
 - Plasma Free Hemoglobin*
 - Platelet Count

Medtronic Controlled Information

- Reticulocytes Count
- Haptoglobin
- Serum lactate dehydrogenase (LDH)
- Serum Creatinine (at baseline only, to allow for EuroSCORE to be calculated)

*Plasma free hemoglobin (PFH) will be the primary lab result used to diagnose hemolysis; however, if PFH results are inconclusive or not available, serum lactate dehydrogenase, haptoglobin and reticulocyte count may be used together to diagnose hemolysis, and may do so without reporting a protocol deviation. If neither PFH nor the combination of serum lactate dehydrogenase, haptoglobin and reticulocyte count are completed, the site must report a protocol deviation.

6.5.2 Hemostasis

The following blood labs are required for subjects on anticoagulation therapy (as appropriate for the type of anticoagulant):

- International Normalized Ratio (INR)
- Activated Partial Thromboplastin Time (aPTT)
- Prothrombin Time (PT)

For subjects continuing on anticoagulation therapy, coagulation panels should be performed as part of the follow-up assessments.

6.6 Medications

Use of the following medications will be collected at baseline and at each postoperative interval and recorded on the appropriate eCRF:

- Anticoagulants
- Antiplatelets
- Aspirin (including Carbasalate calcium)

The physician will determine the appropriate anticoagulation therapy for each subject. Except where contraindicated, Medtronic recommends anticoagulation therapy during the initial healing stages after implantation in accordance with normal practices for bioprosthetic valves. Long-term anticoagulant and/or antiplatelet therapy should be considered for subjects with a dilated left atrium, a history of thromboembolic events, or a cardiac rhythm of atrial fibrillation or atrial flutter.

Subjects should be weaned off of anticoagulants per the Investigator's standard clinical practice.

6.7 Vital Status

Medtronic Controlled Information

A vital status (alive or deceased) should be confirmed for trial subjects at the 18 and 30 month phone calls and at trial exit and recorded on the appropriate eCRF.

6.8 Emergency Use

Given the investigational status of the Model 400 valve, and the availability of approved surgical valves, emergency cases are not allowed under this protocol.

6.9 Deviation Handling

A trial deviation is any event in which the trial is not conducted according to the CIP and/or agreement. Deviations may include, but are not limited to the following:

- Failure to obtain informed consent prior to participation
- Incorrect version of the informed consent form used
- Failure to obtain Ethics Board approval before the start of enrolling subjects in the trial
- Implanted subject did not meet inclusion/exclusion criteria
- Required testing and/or measurements not done or incorrectly done
- Subject did not attend follow-up visit
- Follow-up visit was completed outside window
- Unauthorized use of investigational devices
- Adverse events/UADE or device deficiencies not reported in the required timeframe by country regulation or as specified in the CIP
- Control of trial devices not maintained
- Source data permanently lost
- Enrollment of subjects during lapse of Ethics Board approval
- Enrollment limits exceeded

The investigator is not allowed to deviate from the CIP, except when necessary to protect the life or physical well-being of a subject in an emergency situation. Trial deviations must be reported to Medtronic on the Protocol Deviation eCRF.

In the event the deviation involves a failure to obtain a subject's consent, or is made to protect the life or physical well-being of a subject in an emergency, the deviation must be reported to the Ethics Board as well as Medtronic as soon as possible but no later than five (5) working days from the date of the deviation occurrence.

Reporting of all other study deviations should comply with Ethics Board policies and/or local laws and must be reported to Medtronic as soon as possible upon the center becoming aware of the deviation. Reporting of deviations must comply with Ethics Board policies, local laws, and/or regulatory agency

Medtronic Controlled Information

requirements. Refer to Tables 13-18 for geography-specific deviation reporting requirements and timeframes for reporting to Medtronic and/or regulatory bodies.

Medtronic is responsible for analyzing deviations, assessing their significance, and identifying any additional corrective and/or preventive actions which may include amending the CIP, conducting additional training, terminating the investigation, etc. Repetitive or serious investigator compliance issues may represent a need to initiate a corrective action plan with the investigator and site, and in some cases, necessitate suspending enrollment at that site until the problem is resolved or ultimately terminating the investigator's participation in the study. Medtronic may provide center-specific reports to investigators summarizing information on deviations that occurred at the investigational site on a periodic basis.

6.10 Assessment of Safety

6.10.1 Definitions

The definitions to be applied for the purposes of safety reporting are provided in Table 4.

Table 4: Definitions of Adverse Events for the PERIGON Pivotal Trial

Event Type	Definition
Adverse Event (AE) (EN ISO14155:2011 3.2)	Any untoward medical occurrence, unintended disease or injury, or untoward clinical signs (including abnormal laboratory findings) in subjects, users or other persons, whether or not related to the investigational medical device. NOTE 1: This definition includes events related to the investigational medical device or the comparator. NOTE 2: This definition includes events related to the procedures involved. NOTE 3: For users or other persons, this definition is restricted to events related to investigational medical devices.
Serious Adverse Event (SAE) (EN ISO14155:2011 3.37)	Adverse event that 
 a) led to death, b) led to a serious deterioration in the health of the subject, resulting in 
 1) a life-threatening illness or injury, or 2) a permanent impairment of a body structure or a body function, or 3) in-patient or prolonged hospitalization, or 4) medical or surgical intervention to prevent life-threatening illness or injury or permanent impairment to a body structure or a body function, c) led to foetal distress, foetal death or a congenital abnormality or birth defect.

Medtronic Controlled Information

Event Type	Definition
	
NOTE: Planned hospitalization for a pre-existing condition, or a procedure required by the CIP, without serious deterioration in health, is not considered a serious adverse event.

Adverse Device Effect (ADE) or Device-Related Adverse Event (EN ISO14155:2011 3.1)
	
Adverse event related to the use of an investigational medical device.
 
NOTE 1: This definition includes adverse events resulting from insufficient or inadequate instructions for use, deployment, implantation, installation, or operation, or any malfunction of the investigational medical device.
 
NOTE 2: This definition includes any event resulting from an error use or from intentional misuse of the investigational medical device.

Serious Adverse Device Effect (SADE) (EN ISO14155:2011 3.36)
	
Adverse device effect that has resulted in any of the consequences characteristic of a Serious Adverse Event.


Unanticipated Adverse Device Effect (UADE) (21 CFR 812.3)
	
Any serious adverse effect on health or safety or any life-threatening problem or death caused by, or associated with, a device, if that effect, problem, or death was not previously identified in nature, severity, or degree of incidence in the investigational plan or application, or any other unanticipated serious problem associated with a device that relates to the rights, safety, or welfare of subjects.

Unanticipated Serious Adverse Device Effect (USADE) (EN ISO14155:2011 3.42)
	
Serious adverse device effect which by its nature, incidence, severity or outcome has not been identified in the current version of the risk analysis report, or any other unanticipated serious problem associated with a device that relates to the rights, safety, or welfare of subjects.
 
NOTE: Anticipated serious adverse device effect (ASADE) is an effect which by its nature, incidence, severity or outcome has been identified in the risk analysis report.

Device Deficiency (EN ISO14155:2011 3.15)
	
Inadequacy of a medical device with respect to its identity, quality, durability, reliability, safety or performance.
 
NOTE: Device deficiencies include malfunctions, use errors, and inadequate labeling.

Medtronic Controlled Information

Event Type	Definition
Mandatory Problem Reporting Incident (SOR/98-282 59-61.1(2))	An incident that (a) is related to a failure of the device or a deterioration in its effectiveness, or any inadequacy in its labeling or in the directions for use, and (b) has led to the death or a serious deterioration in the state of health of a patient, user or other person, or could do so were it to recur. NOTE: this definition and reporting requirement pertains to events that occur within Canada only.

6.10.2 Evaluation and Documentation of Adverse Events and Device Deficiencies

Investigators are required to assess and document in the medical record all AEs and Device Deficiencies (per the definitions in Table 4) observed in trial subjects from the time they are consented until they are no longer participating in the trial.

All AEs that occur during the trial need to be reported to Medtronic via the AE eCRF. Documented pre-existing conditions are not considered to be reportable unless there is a change in the nature or severity of the condition. Pre-existing events should be reported as Adverse Events in the situation where a new treatment has to be started or an existing treatment has to be changed to treat the adverse event and the event is accompanied with signs and symptoms.

Unavoidable events are conditions which do not fulfill the definition of an Adverse Event, meaning those medical occurrences, clinical signs (including toward abnormal laboratory findings), diseases or injuries that are not untoward in nature, specifically those resulting from the intended injury such as the index surgical aortic valve replacement procedure.

The events in Table 5 below are expected and appropriate to occur with any open heart surgery and therefore do not fulfill the definition of Adverse Event, and do not need to be reported as Adverse Events, unless they occur outside of the stated timeframe, are otherwise considered to be an Adverse Event according to the treating investigator, or are suspected or confirmed to be device-related.

Table 5: Non-Reportable Medical Occurrences associated with Index Procedure

Body category	Occurrence	Timeframe (hours) from the Index Procedure
Hematologic	Blood transfusion and anemia occurring during the index procedure within expected ranges (part of the regular hospital protocol)	0
Hematologic	Any bleeding during the index procedure	0
Hematologic	Any bleeding after index procedure with < 3 units blood transfusion, or < 1 liter blood loss	24
Cardiac	Short transient episode of arrhythmia (including ventricular fibrillation) during index procedure	0
Central nervous system	Confusion, anxiety and/or disorientation (other than TIA/stroke) starting within 48 hours with or without medical intervention	120 (5 days)
Central nervous system	Temporary change in mental status (other than TIA/stroke) not requiring additional medical interventions or new medical assessments (e.g. CT)	72
Central nervous system	Dizziness and/or lightheadedness with or without treatment	24
Central nervous system	Headache with or without treatment	72
Central nervous system	Sleep problems or insomnia with or without treatment	120 (5 days)
Respiratory/pulmonary	Mild dyspnea or cough with or without treatment	72
Respiratory	Oxygen supply after extubation / “forced breathing therapy”	48
Gastrointestinal	Diarrhea with or without treatment	48

Medtronic Controlled Information

Gastrointestinal	Obstipation / Constipation with or without treatment	72
Gastrointestinal	Anesthesia-related nausea and/or vomiting with or without treatment	24
Body Temperature	Low-grade fever (<101.3°F or <38.5°C) without confirmed infection	48
Body Temperature	Low body temperature	6
Pain	Pain (e.g. back, shoulder) related to laying on the procedure table with or without treatment	72
Pain	Incisional pain (pain at access site) with or without standard treatment and patient not returning to clinic to have additional treatment	No time limit
Pain	Pain in throat and/or trachea due to intubation	72
Skin and subcutaneous System	Mild to moderate bruising or ecchymosis	168 (7 days)
Respiratory	Atelectasis / Pleural Effusion not requiring punctuation	168 (7 days)
General	Edema resulting in weight increase up to 4 kg / 9lbs from baseline	168 (7 days)

- The general process for reporting Adverse Events is as follows: Report the event to Medtronic as soon as possible but no later than the timeframes outlined in Table 7. Sites will be provided with the contact information of the appropriate Medtronic designee.
- Complete all sections of the Adverse Event eCRF.
- Each unique event/diagnosis must be documented separately.
- Documented pre-existing conditions are not considered to be reportable AEs unless there is a change in the nature or severity of the condition.
- The Adverse Event eCRF must be reviewed and approved by the Investigator.

Medtronic Controlled Information

The following information should be collected on the Adverse Event eCRF:

- Date of onset or first observation
- Date of first awareness by investigator
- Description of the event
- AE code number (provided by Medtronic)
- Seriousness of the event
- Causal relationship of the event to the Model 400 valve
- Causal relationship of the event to the TruSize™ Sizer or Valve Handle
- Causal relationship of the event to the implant procedure
- Action taken, including any medical or surgical intervention and date of intervention
- Outcome or status of the event; any reported event should be followed until it has resolved, has a stable level of sequelae, or is no longer clinically significant in the investigator’s opinion

In addition, for all endpoint-related adverse events and deaths, sites should submit relevant, de-identified source documents to Medtronic for the Clinical Events Committee (CEC) members to use in their adjudication of the event. The CEC may request source documentation on additional events, at their discretion and according to the CEC Charter. Additional information regarding the CEC is detailed in Section 16.4.1.

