7.1.1.1 Endpoints

Safety of the valve will be evaluated by the time-related incidence of valve-related adverse events and death. The following valve-related adverse events will be evaluated in this study: Thromboembolism, Thrombosis, Hemorrhage (all and major), Paravalvular leak (PVL, all and major), Endocarditis, Hemolysis, Structural valve deterioration, Non-structural dysfunction, Reintervention, Explant, and Death.

Definitions for the above valve-related adverse events are located in Appendix E.

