7.1.1.4 Analysis Methods

Primary endpoint analyses for regulatory approval will be done on consecutive subjects, and according to the requirements of the guidance documents:

- ISO5840:2009: for regulatory submissions in geographies adhering to the ISO5840:2009 standards (minimum of 150 subjects with 1 year follow up and 400 patient years)
- FDA Heart Valve Guidance 2010 for US FDA PMA (minimum of 300 subjects with 1 year follow up and 800 patient years).

Early rates of adverse events will be calculated as the number of early adverse events divided by the total number of subjects, expressed as a percentage. Early events are events occurring on or before 30 days post-operative.

Linearized rates will be calculated as the number of late events divided by the cumulative late post-operative patient-years, expressed as a percentage. Late events are events occurring after 30 days post-operative. For those adverse events with OPC available, the linearized rates and their associated one-sided upper 95% confidence bounds will be compared to 2 x the OPC rate to show that they are within acceptable limits.

Kaplan-Meier survival analyses will also be performed to summarize the adverse event data.

In addition, control articles based on current literature of previously approved heart valves will be selected. Adverse event data from the control articles will be provided so as to inform the reader of the current state of heart valve technology, as expressed by articles in quality peer-reviewed journals, and allow additional evaluation of the Model 400 adverse event data.

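### Table 5 joins its two 24-hour bleeding limits with *or*, so a bleed over one limit may go unreported and early hemorrhage may be counted differently across sites

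*Protocol*

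**What the plan says.** Protocol 6.10.2 lists in Table 5 occurrences regarded as a normal part of open heart surgery and therefore outside the adverse event definition. One row, with a time frame of 24 hours, reads: "Any bleeding after index procedure with < 3 units blood transfusion, or < 1 liter blood loss".

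The sentence introducing the table sets the effect of being listed. Such occurrences "do not need to be reported as Adverse Events, unless they occur outside of the stated timeframe", or they "are otherwise considered to be an Adverse Event according to the treating investigator, or are suspected or confirmed to be device-related".

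Hemorrhage, both all and major, is one of the safety endpoints in Protocol 7.1.1.1. On how it is defined, that section says: "Definitions for the above valve-related adverse events are located in Appendix E". Appendix E is not in the text available for this review. The protocol's revision history records that it was updated in version 1E to clarify the reporting of bleeding.

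Protocol 7.1.1.4 sets up two rates. For events up to day 30: "Early rates of adverse events will be calculated as the number of early adverse events divided by the total number of subjects". Events after day 30 go into a linearized rate per late patient-year, and only that rate is compared with twice the OPC. SAP 7.9.1.3.1 repeats the early and late split and adds Kaplan-Meier summaries of valve-related events. SAP 7.1.3 starts the clock at the procedure date.

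**The concern.** Two numeric limits in one row suggest an intention to exempt only ordinary post-operative bleeding. Joined by *or*, neither number acts as a cap. Blood loss is unbounded if fewer than 3 units are given, and transfusion is unbounded if recorded loss stays under 1 liter. Elsewhere in the same table, the incisional pain row has a further condition to meet and attaches it with *and*.

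The row can also be read in two ways. A site that takes it literally and a site that assumes both limits must hold would each believe it was following the plan, yet would report different bleeds.

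At stake are the completeness and between-site comparability of early hemorrhage, a named safety endpoint reported to regulators. A bleed that is never reported does not reach the Clinical Events Committee through the process described. SAP 7.3 also tests for a site effect on valve-related events with a threshold of p = 0.15. Different readings of one reporting rule could create or hide such an effect.

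**Working it through.** The plan states no early hemorrhage rate or expected count, so there is no figure to reproduce. The check is of the rule's logic, and then of which analyses a first-day bleed can enter.

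**Step 1. The four combinations** (limits from Table 5; at or above a limit counts as exceeding it)

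| Units transfused | Blood loss | Exempt under *or* | Exempt under *and* |
|---|---|---|---|
| < 3 | < 1 L | yes | yes |
| < 3 | ≥ 1 L | yes | no |
| ≥ 3 | < 1 L | yes | no |
| ≥ 3 | ≥ 1 L | no | no |

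Three of four combinations are exempt under *or*, one of four under *and*. The two readings differ in the two discordant rows.

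**Step 2. What brings a discordant bleed back into reporting.** Within the 24 hours there are two routes: the treating investigator considers it an adverse event, or it is suspected or confirmed to be device-related. Protocol 6.10.3 classifies relation to the implant procedure separately from relation to the device, so a link to the procedure alone does not lift the exemption.

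**Step 3. Whether seriousness brings it back.** Table 4 in Protocol 6.10.1 counts as serious an event that led to "medical or surgical intervention to prevent life-threatening illness or injury or permanent impairment" of a body structure or function. A discordant bleed could fit that wording. But a serious adverse event is defined there as a kind of adverse event, and Protocol 6.10.2 says listed occurrences are not adverse events. Seriousness does not by itself override the row; the investigator's judgement has to do so.

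**Step 4. Whether a later step would find it.** Under SAP 7.9.1.3.1 the investigator identifies and reports events, and the committee then reviews them. Protocol 16.4.1 describes adjudication of deaths and potential endpoint events. It states no search for unreported Table 5 bleeds.

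**Step 5. Which results are exposed.**
- Early rate (Protocol 7.1.1.4): exposed, but only for the first 24 hours of a 30-day window.
- Kaplan-Meier (SAP 7.2.2.4 and 7.9.1.3.1): exposed. The clock starts at the procedure. If the omitted bleed meets the hemorrhage definition and the subject has no other hemorrhage, every estimate from 30 days to five years is affected.
- Late linearized rate against twice the OPC: not exposed. It counts only events after day 30, so the number of 24-hour bleeds that can enter it is 0.

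**Step 6. Size.** Let *s* be the share of true early hemorrhages that are discordant, fall within 24 hours and go unreported. Then

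counted early rate = true early rate × (1 − *s*).

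Neither term is given in the documents. With assumed values only:

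| Assumed true early rate | *s* = 0 | *s* = 10% | *s* = 25% | *s* = 50% |
|---|---|---|---|---|
| 2% | 2.0% | 1.8% | 1.5% | 1.0% |
| 5% | 5.0% | 4.5% | 3.75% | 2.5% |

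For example, 5% × (1 − 0.25) = 3.75%. The table shows how the rate would respond; it is not an estimate. Nothing in the documents excludes *s* = 0.

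**The case against.** The strongest reply is that this is a wording ambiguity with safeguards around it.

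- *The exemption is not absolute.* Once the investigator considers a bleed an adverse event, reporting is required. A surgeon facing a bleed that needed intervention to avert a life-threatening state would be expected to do so. This stands: such bleeds cannot be called simply non-reportable. But it leaves ascertainment to judgement, which may vary between sites.
- *The definition is in Appendix E.* It may already settle the row, or may exclude surgical bleeding on the first day. Protocol 8.2.2 describes the hemorrhage risk as related to anticoagulant or antiplatelet treatment, which points the same way. This also stands: no loss of endpoint events can be asserted without that text. The need to reconcile remains, because a stricter Appendix E would conflict with the row and a silent one would leave the gap open.
- *Monitoring.* Protocol section 12 provides full source verification through market approval, and 12.2 has monitors check reporting. This helps only in part, since an omission that complies with Table 5 as written is not an error to be found.
- *Reach.* Protocol 1.2 reports that sizes 19 to 27 mm were approved in the US, Canada and Europe in 2017, and 2.1 ends enrollment in a geography as sizes are commercialized there. A change may reach few new index procedures and would put one cohort under two wordings. This stands, and is why the fix includes a statement in the report.

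A reader might infer that the early hemorrhage rate is under-counted, or attach a number of missed events. The documents support neither: they give no early bleeding rate, no share of discordant bleeds and no record of how sites read the row.

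**Conclusion.** The point holds as a defect in a reporting rule. Read literally, a 24-hour bleed that exceeds one of the two limits need not be reported unless one of the two exceptions in Step 2 applies. The alternative reading is plausible enough that compliant sites may differ.

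The consequence is a possible one: a lower, or unevenly ascertained, early hemorrhage rate and Kaplan-Meier estimate. It requires that a discordant bleed would meet the Appendix E definition and that neither exception was used. What can be derived is the change from three of four exempt combinations to one of four; the effect on any rate cannot be computed, and its lower bound is zero.

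A reader might also infer that the primary safety comparison is compromised. It is not, because that test uses only events after 30 days. The early rate is descriptive and carries no hypothesis test. The change is still worth making, because hemorrhage is a named safety endpoint and the correction is small.

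**What to change.** Reword the Table 5 row so that the exemption applies only when both limits are respected, that is, replace *or* with *and*. Check the row against the hemorrhage definition and bleeding reporting rules in Appendix E, and make the two agree.

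For subjects already implanted, state in the report which reading sites applied. Where source records allow, also check first-day bleeds that exceeded one limit.

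The wording change costs one word in an amendment, plus some additional adverse event forms and committee reviews. Its reach is limited if few index procedures remain, and events before and after it would have been collected under different wording, which the report should say. A retrospective check would need chart review at up to 40 sites, so it is an option rather than a condition of the fix.
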